| Visit Day(s)                                                                        | -28 to 1  | 1                 | 8 b | 15                        | 29                        | 85                        | 183                       | 365            |                         |
| Visit Window                                                                        |           |                   | +3 d           | +3 d                      | +7 d                      | +7 d                      | ±14 d                     | ±1 m           |                         |
| Visit Type                                                                          | SCREENING | STUDY VACCINATION | Safety         | Safety and Immunogenicity | Safety and Immunogenicity | Safety and Immunogenicity | Safety and Immunogenicity | Immunogenicity | Early Exit              |
| Approximate daily blood draw, mL                                                    |           | 26                |                | 26                        | 26                        | 26                        | 26                        | 26             | 26                      |
| Approximate cumulative study blood draw, mL                                         |           | 26                | 26             | 52                        | 78                        | 104                       | 130                       | 156            |                         |
| Blood draw volumes:                                                          |           |                   |                |                           |                           |                           |                           |                |                         |
| Participants with blood draws for both humoral and cellular responses (N=80) |           |                   |                |                           |                           |                           |                           |                |                         |
| Approximate daily blood draw, mL                                                    |           | 86                |                | 86                        | 26                        | 86                        | 86                        | 86             | 86                      |

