| Approximate daily blood draw, mL                                                     |           | 26                  |                | 26                        | 26                        | 26                        | 26                        | 26                                 |                   | 26                        | 26                        | 26                        | 26                        | 26              | 26              | 26              | 26              | 26                      |
| Approximate cumulative study blood draw, mL                                          |           | 26                  | 26             | 52                        | 78                        | 104                       | 130                       | 156                                | 156               | 182                       | 208                       | 234                       | 260                       | 286             | 312             | 338             | 364             |                         |
| Blood draw volumes:                                                           |           |                     |                |                           |                           |                           |                           |                                    |                   |                           |                           |                           |                           |                 |                 |                 |                 |                         |
| Participants with blood draws for both humoral and cellular responses (N=160) |           |                     |                |                           |                           |                           |                           |                                    |                   |                           |                           |                           |                           |                 |                 |                 |                 |                         |

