| 
 
To assess the safety and reactogenicity of the selected RSV.preF-based vaccine formulation (based on Cohort 1 and 2 results), compared to the formulation to be used for future clinical development
 
 | 
 
SAEs and AESIs from first administration until 6 months after the last vaccination
 
Solicited local and systemic AEs for 7 days after each vaccine administration
 
Unsolicited AEs from the time of each vaccine administration through the following 28 days
 
 |
| SECONDARY                                                                                                                                                                                                                                       |                                                                                                                                                                                                                                                                                                                                 |
| 
 
To assess immune responses to the selected RSV.preF-based vaccine formulation (based on Cohort 1 and 2 results), compared to the formulation to be used for future clinical development
 
              | 
 
RSV neutralization antibody titers
 
                                                                                                                                                                                                                                            |
| 
 
To assess the durability of the immune response to the selected RSV.preF-based vaccine formulation in groups with and without revaccination
 
                                                          | 
 
RSV neutralization antibody titers
 
                                                                                                                                                                                                                                            |

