### Expanded Safety Cohort (Cohort 3)

In the expanded safety cohort, approximately 400 participants will be randomized in parallel to 1 of 5 arms (in a 6:3:3:2:2 ratio to Arms 10, 11a, 11b, 12, and 13; [Table 7](#)). No pauses in enrollment for safety assessments are planned. Participants will receive either the selected 2×1 mL formulation based on the results from Cohorts 1 and 2, the selected 1 mL formulation for future clinical development, placebo, or the current Ad26/protein preF RSV vaccine (1×10^11 vp Ad26.RSV-A.preF/150 µg RSV-A preF protein).

Vaccine components evaluated in Cohorts 1 and 2 will be administered as 2 IM injections of 1 mL in the same deltoid muscle. However, once the optimal composition is selected, manufacturing formulation will be adjusted to ensure the administration of a single 1 mL vaccine dose in subsequent cohorts. Participants in Arms 11a and 11b will receive the selected vaccine in a 1 mL formulation and a second injection with placebo (1 mL) for blinding purposes. Cohort 3 thus will compare the 2×1 mL formulation of the selected combination of RSV vaccine components from Cohorts 1 and 2 (Arm 10) with the 1 mL formulation to be used for future clinical development (Arms 11a and 11b) with follow-up for 1 year post-vaccination in a double-blind placebo-controlled fashion. Participants in Arm 13 will receive the current Ad26/protein preF RSV vaccine (1×10^11 vp Ad26.RSV-A.preF/150 µg RSV-A preF protein) in a 1 mL formulation and a second injection with placebo (1 mL) for blinding purposes. Participants in Arms 11a, 11b and 12 will continue the study to assess durability and the effect of revaccination with follow-up up to 5 years post first vaccination. The timing of revaccination (at least 12 months relative to the first dose) will be based on Ad26/protein preF RSV vaccine clinical data.

For a subset of the participants, additional cellular immunogenicity assessments will be performed. This subset will be referred to as the Cellular Immuno Subset and will consist of approximately 240 participants: 40 participants per arm in Arms 10, 12 and 13, and 60 participants per arm in Arms 11a and 11b. The Cellular Immuno Subset will be recruited in study sites that have PBMC collection capability.

VAC18195 (JNJ 64400141/ JNJ 64213175/ JNJ-86051823/ JNJ 78991172)

Clinical Protocol VAC18195RSV1001 Original

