### **6.3. Measures to Minimize Bias: Randomization and Blinding**

#### **Study Vaccine Allocation**

##### *Procedures for Randomization*

Central randomization will be implemented in this study. Participants will be randomly assigned to a vaccination group, as described in Section 4.1, based on a computer-generated randomization schedule prepared before the study by or under the supervision of the sponsor. The randomization will be balanced by using randomly permuted blocks.

Sites will be split into 2 categories based on their PBMC collection capabilities for enrolment in the Cellular Immuno Subset.

For Cohorts 2 and 3, sites collecting PBMC samples will randomize participants in the Cellular Immuno Subset of the respective cohort in a ratio as described in Section 4.1. These sites may enroll participants without PBMC sampling on the same day once their daily PBMC capacity has been reached. PBMC samples will be collected for all participants in Cohort 1 and for 38 participants per arm in Cohort 2. In Cohort 3 PBMC samples will be collected for approximately 240 participants: 40 participants per arm in Arms 10, 12, and 13, and 60 participants per arm in Arms 11a and 11b. When the Cellular Immuno Subset has been completed for a cohort, the sites will continue randomizing the remaining participants without PBMC sampling. Sites with no PBMC sample collection capabilities will randomize participants that are not part of the Cellular Immuno Subset. Separate randomization lists will be used for the Cellular Immuno Subset and for the participants that are not part of the Cellular Immuno Subset.

The interactive web response system (IWRS) will assign a unique intervention code, which will dictate the intervention assignment and matching study vaccine kit for the participant. The requestor must use his or her own user identification and personal identification number when contacting the IWRS, and will then give the relevant participant details to uniquely identify the participant.

---

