##### **9.4.3. Immunogenicity Analyses**

Immunogenicity data of corresponding arms from Cohort 1 and Cohort 2 will be combined in all analyses. Immunogenicity data of corresponding arms from Cohort 3 and Cohort 4 will be combined as applicable.

Continuous variables will be summarized descriptively. For continuous parameters, descriptive statistics of the actual values will be calculated at all timepoints, including geometric mean with 95% CI, median and quartiles, as applicable. Additionally, geometric mean fold rises from baseline and corresponding 95% CIs might be calculated.

For combined primary endpoint data of Cohort 1 and Cohort 2, geometric mean ratios between each active arm and Arm 1b will be calculated at all available timepoints, with corresponding 95% CI, as applicable. For Cohort 3, Arms 11a and 11b will be combined and the active arms will be compared to each other at all available timepoints up to 1 year after vaccination on Day 1, by means of geometric mean ratios with corresponding 95% CI. For durability and revaccination evaluation Arm 11a (Cohort 3) and Arm 14 (Cohort 4) will be combined, Arm 11b (Cohort 3) and Arm 15 (Cohort 4) will be combined, and Arm 12 (Cohort 3) and Arm 16 (Cohort 4) will be combined.

For immunogenicity analyses, baseline is considered as the last assessment pre-vaccination. Graphical representations of immunologic parameters will be made as applicable.

Geometric means per arm, and geometric mean ratios between active arms, with corresponding 95% CIs will be estimated via an analysis of variance (ANOVA) including all active arms, using log-transformed post-vaccination immune parameter response as dependent variable and study arm as independent variable. The means and differences in mean and CIs will be back-transformed (by exponentiation) to CIs around a GMT or geometric mean titer ratio (GMR). This analysis will be performed for all available assays and all time points, separately per assay. Data of the same arms from different cohorts will be combined, as applicable.

As a sensitivity analysis, the ANOVA may also be performed adjusting for the respective baseline titers, by including baseline titer as additional covariate.

For categorical variables, frequency tables will be presented.

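### Cohort 3 pools two randomisation lists that supply 27% of Arm 10 but 80% of every other arm, and no planned titre or safety comparison accounts for the list

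*Protocol*

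**What the plan says.** Protocol 6.3 divides sites by whether they can collect PBMC samples and keeps two lists: "Separate randomization lists will be used for the Cellular Immuno Subset and for the participants that are not part of the Cellular Immuno Subset". Three rules decide who goes on which list:

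- Sites without PBMC capability feed only one list: "Sites with no PBMC sample collection capabilities will randomize participants that are not part of the Cellular Immuno Subset".
- PBMC sites can feed both lists on one day: "These sites may enroll participants without PBMC sampling on the same day once their daily PBMC capacity has been reached".
- Once the subset is full, PBMC sites also enrol only to the second list.

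For Cohort 3, Protocol 4.1 sets the subset at "40 participants per arm in Arms 10, 12 and 13, and 60 participants per arm in Arms 11a and 11b", about 240 in all. Protocol 6.3 repeats these counts. The schedules in Protocol 1.3.2 and 1.3.3 agree, with N=80 for Arms 10 and 13 and N=160 for Arms 11a, 11b and 12. Table 7 gives arm sizes of 150/75/75/50/50.

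Protocol 9.4.3 estimates geometric means and their ratios by ANOVA "using log-transformed post-vaccination immune parameter response as dependent variable and study arm as independent variable", and SAP 5.3.3 does the same. An optional sensitivity model adds baseline titre (Protocol) or baseline titre, age and sex (SAP). SAP 5.3.2 summarises safety by cohort and arm, and SAP 5.8.4 plans no subgroup analysis. No titre or adverse event analysis uses list, subset membership or site type.

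**The concern.** Randomisation protects a comparison within a list. It protects a comparison pooled over lists only if the allocation ratio is the same in each list or the analysis conditions on list. Neither holds for Arm 10.

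The contrast exposed is the central one. The Cohort 3 primary objective begins "To assess the safety and reactogenicity of the selected RSV.preF-based vaccine formulation (based on Cohort 1 and 2 results), compared to the formulation", which is Arm 10 (2×1 mL) against Arms 11a+11b (1 mL). The first secondary objective makes the same comparison for neutralising titres. Arm 10 versus Arm 13, and for safety Arm 10 versus placebo Arm 12, are exposed in the same way.

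List membership is partly tied to site type, daily laboratory capacity and enrolment order. Subset members also give 86 mL rather than 26 mL of blood on Day 1 and Day 15. If any of these is related to titre or to adverse event reporting, part of that relation would be read as a formulation effect. The imbalance follows from the planned counts, so a larger sample with the same proportions would not remove it.

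**Working it through.** **Inputs.** Arm sizes and subset counts as above. SD of RSV-A2 neutralising titre 1.3 on the log2 scale (Protocol 9.2.2). The list effect is not given, so it is assumed over a range.

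**The plan's own figures.** 400 × (6,3,3,2,2)/16 = 150/75/75/50/50, and 40+60+60+40+40 = 240. Both match. With SD 1.3 and 55 per arm, the t-based interval for a ratio of 1 is 0.71 to 1.41, as in Table 14.

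**Composition of the arms.** The second list is obtained by subtraction.

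| Arm | Total | Subset list | Second list | Subset share |
|---|---|---|---|---|
| 10 | 150 | 40 | 110 | 26.7% |
| 11a | 75 | 60 | 15 | 80% |
| 11b | 75 | 60 | 15 | 80% |
| 12 | 50 | 40 | 10 | 80% |
| 13 | 50 | 40 | 10 | 80% |

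The chance of being assigned to Arm 10 is 40/240 = 16.7% on the subset list and 110/160 = 68.8% on the other.

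**Bias.** For an additive list effect d, an arm-only contrast with Arm 10 is off by (0.800 − 0.267) × d = 0.533d. The direction depends on the sign of d.

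**Titres.** The arm-only SE is 1.3 × √(1/150 + 1/150) = 0.150 for Arm 10 versus 11a+11b, and 1.3 × √(1/150 + 1/50) = 0.212 for Arm 10 versus 13. With b = 0.533d, coverage = Φ(1.96 − b/SE) − Φ(−1.96 − b/SE).

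| Assumed d (log2) | Bias b | Spurious ratio, 2^b | Coverage, 10 vs 11a+11b | Coverage, 10 vs 13 |
|---|---|---|---|---|
| 0.10 | 0.053 | 1.04 | 93.5% | 94.3% |
| 0.25 | 0.133 | 1.10 | 85.6% | 90.4% |
| 0.50 | 0.267 | 1.20 | 57.3% | 75.9% |

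**Safety.** An assumed gap of 2, 5 or 10 percentage points in an event rate between lists gives a spurious arm difference of 1.1, 2.7 or 5.3 points.

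**Cost of adjusting.** In the model with Arms 10, 11a+11b and 13 plus list, the variance of the list coefficient is 1.3² / (40×110/150 + 120×30/150 + 40×10/50) = 1.69/61.33, an SE of 0.166. Each Arm 10 contrast gains 0.533² times that variance:

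- Arm 10 versus 11a+11b: SE 0.150 becomes 0.174 (ratio 1.16), and the 95% interval goes from ×/÷1.23 to ×/÷1.27.
- Arm 10 versus 13: SE 0.212 becomes 0.230 (ratio 1.08), and the interval goes from ×/÷1.33 to ×/÷1.37.
- 11a+11b versus 13: unchanged.

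**Break-even.** The arm-only estimate has the smaller mean squared error when (0.533d)² is below the added variance, that is for d below about 0.17 log2 (2^0.166 = 1.12, about 12% in titre).

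**Not affected.** Within Cohort 3, contrasts among Arms 11a, 11b, 12 and 13 (80% in each). In Cohort 2, all contrasts (38 of 48 in every arm). ELISpot and ICS lie wholly within the subset list.

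**The case against.** The strongest objection is that this is exposure to bias and not demonstrated bias. Nothing in the documents gives a titre or safety difference between lists. PBMC capability is a sample-processing property, and every size above is an assumed input times 0.533. A 0.5 log2 effect means a 41% difference in titre, and the documents do not favour that over a much smaller one. Below about 0.17 log2 the planned estimator is the more accurate. No hypothesis is tested, and the formulation is selected from Cohorts 1 and 2. Fold increase from baseline and the optional covariates would absorb some of a list effect. All of this stands and limits the severity. It does not restore the protection of randomisation: the covariate model is optional, and neither it nor fold increase covers site type, enrolment time or adverse event reporting.

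A second objection is that Protocol 6.3 refers to the ratio in Section 4.1. If that meant 6:3:3:2:2, a subset of 240 would split 90/45/45/30/30 and the imbalance would vanish. But Section 4.1 itself gives 40 and 60 per arm, Protocol 6.3 repeats those counts, and the schedule totals of 80 and 160 agree. The ratio for the second list is nowhere stated, so the wording should be made explicit.

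Two points of scope also stand. In the durability analyses that pool Cohorts 3 and 4, subset shares are 60/300 = 20% for 11a+14 and 11b+15, against 40/140 = 28.6% for 12+16, so the gap there is only 8.6 points. Safety rates within the second list would rest on 30 participants in 11a+11b and 10 in each of Arms 12 and 13, so the separate rates will be unstable.

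**Conclusion.** The concern holds. On the stated counts, 53.3% of any difference between the two lists passes into every Cohort 3 contrast with Arm 10, and none of the planned titre or safety comparisons removes it. For list effects of 0.10 to 0.5 log2 the ratio for Arm 10 versus 11a+11b would be off by about 4% to 20%. These sizes assume an additive list effect, SD 1.3 log2 and no dropout; the true list effect is unknown and may be negligible. Since the analysis is descriptive, the consequence is a formulation estimate that cannot be separated from a list difference, not an error in a test. The point should be fixed, because the remedy is cheap and the contrast is the main one in Cohort 3.

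**What to change.** - **SAP 5.3.3:** add randomisation list (Cellular Immuno Subset yes/no) as a fixed factor in the Cohort 3 models for geometric means and ratios. Keep the arm-only model as a sensitivity analysis.
- **SAP 5.3.2:** for Arm 10 versus 11a+11b, present safety rates within each list and combined with common weights. Mantel-Haenszel weights are 40×120/160 = 30 and 110×30/140 = 23.6, or 56% subset list and 44% second list. The same layout can serve Arm 10 versus 12 and 13, where the combined figure matters more than the small second-list rates.
- **Protocol 6.3:** state the allocation ratio of each Cohort 3 list, so that the reference to Section 4.1 cannot be read as 6:3:3:2:2 within the subset.

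Allocation, subset sizes and study conduct do not change. List membership is fixed at randomisation and should be recoverable from the IWRS. The price is precision: log-scale intervals about 16% wider for Arm 10 versus 11a+11b and about 8% wider for Arm 10 versus 13, and a larger mean squared error if the true list effect is below about 0.17 log2. In return, the estimate no longer depends on that unknown.

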**Blinding**

The investigator will not be provided with randomization codes. The codes will be maintained within the IWRS, which has the functionality to allow the investigator to break the blind for an individual participant.

For the sponsor, unblinding (at the participant level) of Cohort 1 and 2 will occur at the time of the primary analysis (Section 9.5). From the primary analysis onwards, group level results of Cohort 1 and 2 may be shared as needed, however, efforts will be made to preserve the blinding to the individual participant allocation. Sponsor unblinding (at the participant level) of Cohort 3 will occur at the time of the interim analysis when all participants in Cohort 3 have completed their 28-day post-first vaccination visit (Section 9.5). From this interim analysis onwards, group level results from Cohort 3 may be shared as needed, however, efforts will be made to preserve the blinding to the individual participant allocation (for participants in Arms 11a, 11b, and 12). Sponsor unblinding (at the participant level) of Cohort 4 will occur at the time of the interim analysis when all participants in Cohort 4 have completed their 28 days post-first vaccination visit (Section 9.5). From this interim analysis onwards, group level results from Cohort 4 may be shared as needed, however, efforts will be made to preserve the blinding to the individual participant allocation.

Data that may potentially unblind the randomization group assignment (eg, immunogenicity data, study vaccine preparation/accountability data, study vaccine allocation) will be handled with special care to ensure that the integrity of the blind is maintained and the potential for bias is minimized. This can include making special provisions, such as segregating the data in question from view by the investigators, clinical team, or others as appropriate until the time of database lock and unblinding.

Under normal circumstances, the blind must not be broken for a cohort until all participants in that cohort have completed the study and the database is finalized for the cohort, except for Cohort 3: the blind will be broken for participants in Arms 10 and 13 once all participants in these arms have completed their last visit after 1 year of follow-up post-vaccination. The investigator may, in an emergency, determine the identity of the randomization group by contacting the IWRS. While the responsibility to break the intervention code in emergency situations resides solely with the investigator, it is recommended that the investigator contact the sponsor or its designee if possible, to discuss the particular situation, before breaking the blind. Telephone contact with the sponsor or its designee will be available 24 hours per day, 7 days per week. In the event the blind is broken, the sponsor must be informed as soon as possible. The date, time, and reason for the unblinding must be documented by the IWRS, in the appropriate section of the eCRF, and in the source document. The documentation received from the IWRS indicating the code break must be retained with the participant's source documents in a secure manner.

Participants who have had their intervention assignment unblinded should continue to return for scheduled evaluations.

In general, randomization codes will be disclosed fully only if the study is completed and the clinical database is closed. However, if an interim analysis is specified (Section 9.5), the randomization codes and, if required, the translation of randomization codes into vaccine and control groups will be disclosed to the sponsor and only for those participants included in the interim analysis.

Participants who withdraw will not be replaced.

